**PROPOSAL FOR VALIDATION OF AN INVESTIGATIONAL
DRUG IN
PURASTHA KOLAPERUKKAM
(BENIGN PROSTATIC HYPERPLASIA)**

CLINICAL PROTOCOL: Summary Information

Clinical Protocol Title:

Validation of *investigational drug* in *Purasthakolaperukkam* [Benign Prostatic Hyperplasia]

Protocol number:

Version number and date:

Phase of clinical investigation:

Phase - 2

Investigational drug(s):

Sponsor:

Study Monitor:

Investigator(s):

Clinical Laboratory (ies), Technical Department(s), and Institution(s) Providing Clinical Study Services:

Introduction:

1.1 Background:

Neer arugal noigal described in Siddha literatures are clinical conditions related to disorders with decreased urine output. *Neer kattu* (Retention of urine), *Neer churukkuor* *Neer kricharam* (Oliguria), *Sottu neer* (Dripping of urine), *Neer adaippu* (Anuria) are classified under this category. The above said symptoms except *Neer adaippu* occurs in *Purasthakolaperukkam* [Benign prostatic hyperplasia]. *Pitha Neer Churukku* has been described by the author Yugi in *Yugivaidya chintamani*. Some of the symptoms in this poem may be compared with the symptoms of *Purastha kolaperukkam* (Benign Prostatic Hyperplasia - BPH). The symptoms which occur due to obstruction in the prostatic urethra as in BPH are closely related to those described in the following poem:

அழல் நீசருக்கு

"தான்மூத்திர மஞ்சளித்து மிகச்சி வக்குந்
தளர்ந்குமீம ளககாலு மசதி யாகும்
பானருக்கிச் சிறுகலா யருவி பாயும்
பாரமாங் குதமண்ட மிலிங்கந் தானுங்
கான்வாயு தான்மீறி வயிறு முப்பும்
களகளென்று இளரச்சலாய்க் கசங்கி யேறும்
மீவன்காயு வாயுலர்ந்து மிரட்சி யாகும்
விடும்பித்த மூத்திரத்தின் விவரந் தானே"

- யுகி வைத்திய சிந்தாமணி பாடல் - 739¹

It says that

- yellowish discolouration of the urine,
- reduced stream of the urine,
- bladder distension,
- body tiredness,
- dryness of the mouth are the symptoms of *Pitha Neer churukku*.

The classical preparation XXX is taken up as new Investigational drug in this clinical study. This preparation is widely used by Siddha physicians for various clinical conditions related to the problems of lower abdomen and genitalia. Some Siddha Physicians have reported with evidence that it acts on *Purasthakola perukkam* and reduces the clinical symptoms appreciably.

The current medical practice produces serious side effects such as Impotence, decreased libido, decreased quantity of semen at ejaculation, gynecomastia, asthenia, hypotension, dizziness, somnolence, fatigue, dyspnea and upper respiratory tract infection. When medication fails surgical intervention is needed but this is costly in practice. Moreover, at present herbal remedies like Saw Palmetto (*Serenoa repens*) produces good results in reducing the complaints of the BPH patients. Literary evidences reveal Siddha formulations are being practiced since ages. In exploring the efficacy of Siddha medication for this particular condition evaluation of a new investigational drug is indispensable.

1.2 Rationale:

The investigational new drug (IND) though a classical preparation, is going to be tested for new indication. So it falls under new chemical entity (NCE). Hence, as per AYUSH guidelines safety study is intended. The approval will be sought from the Institutional Animal Ethical Committee and the Safety studies will be done at Department of Pharmacology, SCRI, Chennai.

Another drug XXX is taken up for another one arm and its efficacy is compared with that of XXX. XXX is a well known Siddha drug and it is in practice since time immemorial. Its indication suits the clinical condition Neer kattu (Retention of urine). Since it is a classical drug which is going to be put into trial, preclinical study is not mandatory. [Ref: ICMR Guidelines& WHO Guidelines]

A sample size of twenty patients from OPD of CCRS Institutes will be randomized and put in two arms as open labeled study. The suitable participants as per inclusion criteria will be enrolled and the trial drugs will be administered orally as mentioned in the classical reference. The duration of the trial period will be three months.

BPH is a common condition that affects aged men. The prevalence of BPH is about 50% of men between 50 to 60 years and more than 90% of men who are older than 80 years old. However, only 25% of men above 50 and 50% of men above 75 are symptomatic.²

Benign prostatic hyperplasia (BPH) is a histological diagnosis that refers to the proliferation of smooth muscle and epithelial cells within the prostatic transition zone. It is the most common benign tumor in men and is not a precancerous condition.

BPH causes obstruction of urethra leading to obstructive urinary symptoms-hesitancy, thin urinary stream, intermittent stream and straining to pass urine. Obstruction induced changes in bladder function and age-related changes in both bladder and nervous system function lead to irritative voiding symptoms-urgency, frequency and urge incontinence. There are two components of obstruction-Dynamic and Static. Dynamic obstruction is due to the increase in the tone of smooth muscles of the prostate. The tone of the smooth muscles is mediated by alpha-1 adrenergic receptors and its effects are blocked by alpha-1 adrenergic receptor blockers. The static component of obstruction is due to the mass effect of enlarged prostate which can be counteracted by drugs which causes shrinkage of prostate.²

The specific approach used to treat BPH depends upon number of factors like age, prostate size, weight, prostate-specific antigen level and severity of the symptoms. 5 α -reductase inhibitors decrease the production of dihydrotestosterone within the prostate, which results in decreased prostate volume, increased peak urinary flow rate, improvement of symptoms, decreased risk of acute urinary retention and need for surgical intervention. α_1 -adrenergic receptor (α_1 -AR) antagonists decrease LUTS and increase urinary flow rates in men with symptomatic BPH, but do not reduce the long-term risk of urinary retention or need for surgical intervention. Clinical efficacy of either 5 α -reductase inhibitor or α_1 -AR antagonist has been further improved by using combination therapy; however, long-term outcomes are still awaited. Many more potential new therapies are under development that may improve the treatment of BPH. This article gives a brief account of rationale and efficacy of different treatment options presently available in the management of BPH.

The existing conventional drug treatment has potential side effects like impotence, decreased libido, decreased semen quantity at ejaculation, gynecomastia, asthenia, hypotension, dizziness, somnolence, fatigue, dyspnea and upper respiratory tract infection.

2. Clinical Study Objectives:

2.1 Primary Objective:

To validate the efficacy of the XXX in *Purasthakola perukkam* [Benign prostatic hyperplasia] by measuring the International Prostate Symptom Score.

1.2. Secondary Objectives:

- a) Evaluation of the safety of the investigational drug XXX.
- b) Standardization of process of the XXX.
- c) To assess the effect in the level of PSA, if any.
- d) Exploring Siddha clinical parameters of the clinical condition *Purasthakola perukkam* [BPH].

2. Study Design:

[figure not shown]
Open clinical study

[Randomized, comparative open labeled clinical study]

Since the trial is in two arms, to avoid the bias in the study participants, randomization is opted. The efficacy will be compared with the known Siddha drug XXX. The indication tried with that of XXX is a novel idea, Henceforth the baseline study will be of open labeled.

The expected total duration of subject participation will be six months. Data summarization, Statistical analyzing and monograph preparation will need additional three months. The drug therapy will be of 12 weeks. The follow up will be done without drug on 45th day and 90th day.

3.1 Study design schematic:

3.2 Allocation to treatment:

This clinical study involves two arms. The sample size of subjects is 20. 10 subject each in a single arm. They will be randomized by appropriate method.

3.3 Breaking the blind:

Blinding is not opted as both the trial drugs are classical preparations. The making of placebo is little bit difficult. The study comes under Phase II category. There is lack in published data. Hence an open clinical study is designed.

4. Subject selection:

The proposed clinical evaluation of the investigational new drugs will be done in the OPD's of peripheral Institutes of CCRS. The estimated total number of individuals to be enrolled in this clinical study will be twenty. The subjects to be enrolled will be provided with patient information sheet and informed consent form.

4.1 Subject inclusion criteria:

- Male patients between 40 and 75 years of age.
- Patient diagnosed with BPH and with clinical signs and symptoms of BPH for 3 months.
- Confirmed diagnosis: a) Ultra sonogram study
b) Prostatic Specific Antigen Score 4 ng to 8 ng /mL
[Normal range-PSA Score 0.8 to 4 ng /mL]
- Patient having a post-void residual urine volume of 350 cc.
- Participants who adhere to protocol requirements with written informed consent.

4.2 Subject exclusion criteria:

- PSA score beyond acceptable range and patients with a history of prostate cancer or a serum PSA >8 ng/mL [will be excluded by reviewing the past medical history and the current medication]
- History of urinary urethral obstruction due to stricture, valves, sclerosis or tumor at initiation
- Clinical evidence of prostate cancer at initiation
- Clinical evidence of any of the bladder or urinary tract conditions, which may affect lower urinary tract symptom at initiation
- Patient having a post void residual urine volume 350 cc.
- Patients who have participated in any drug study during the past 3 months
- Any condition which are likely to hinder the compliance with the protocol.

5. Study drug(s):

Arm 1: xxx

(In reference text book the dosage is mentioned as 488 mg, but in this clinical study the dosage is fixed as 100 mg)

[This is given along with milk and administered two times a day after food.]

Arm 2: xxx

[To 20 gram of powder 150 ml of water is added and boiled. It is then filtered and made into decoction. It is administered two times a day before food]

Both the trial drugs will be administered orally. The total drug therapy will be of three months duration.

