5.1.1 Withdrawal of subjects due to non-compliance / adherence

During the course of the trial study period if any serious condition develops which requires urgent treatment such subject may be withdrawn from the trial and managed by the principal investigator accordingly.

5.2 Study drug supplies:

Drugs will be procured from SCRI, Chennai. In case, if there is any difficulty, direction may be given to purchase the trial drugs from any GMP certified firms.

5.2.1 Formulation and packaging:

Each drug will be packaged in the packing paper or polythene cover according to the said dosage. It will be given for 15 days. The review of the participants will be advised accordingly.

5.2.2 Mode of dispensing:

The study drugs will be kept in the co investigator's room and dispensed from there.

5.2.3 Drug administration:

Each study drug will be administered as investigator directed procedure. Specific instructions like do's and don'ts, foods which have to be avoided or added and drug compliance will be given to participant during each review.

5.4 Study drug storage and accountability:

Appropriate storage of the study drugs to ensure their stability will be observed by the investigators. Accountability of the study drugs are also done with documentation. Disposition or other destruction of the study drugs upon completion of the study will be done according to the instructions of the investigators.

5.5 Concomitant Medications:

If any infectious illness occurs to the study participants during the trial period, the concomitant medications will be advised by the investigators.

5.5.2 Rescue Medication:

If any problems occur, rescue medication will be governed by the investigators accordingly.

6. Research Study Procedures:

This study is a randomized, comparative, open-labeled comparing the safety and efficacy of XXX and XXX for 12 weeks in 20 patients with *Purasthakola perukkam* [benign prostatic hyperplasia]. The primary outcome measures will be validating the efficacy of interventional drug with comparator drug by change in Total International Prostate Symptom Score from baseline to end of treatment. The secondary outcomes will be evaluation of the safety of the investigational drug, Process Standardization and exploring Siddha clinical parameters of the clinical condition *Purasthakola perukkam* [BPH].

6.1. Screening procedures:

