QUALITY OF LIFE DUE TO URINARY SYMPTOMS	If you were to spend the rest of your life with your urinary condition just the way it is now, how would you feel about that? (tick one).	0	1	2	3	4	5	6

*International Prostate Symptom Score

IPSSymptom Score= sum of questions A1 to A7

- ◆ Mild Score : 0-7
- ◆ Moderate Score: 8-19
- ◆ Severe Score: 20-35

The Assessment will be made before and after treatment by calculating the International Prostate Symptom Score. Based on this the clinical condition may be divided into mild, moderate and severe. The response will be categorized as mentioned above.

9.1.2 Secondary endpoints:

Measuring Siddha clinical parameters like Envagai thervu, Neerkkuri and Neikkuri

11. Data Handling and Record-Keeping:

11.1 Data recording / Case Report Forms:

A Case Report Form (CRF, see Appendix 1) will be completed for each subject enrolled in the clinical study. The Sponsor-Investigator will review, approve and sign/date each completed CRF; the Sponsor-Investigator's signature serving as attestation of the Sponsor-Investigator's responsibility for ensuring that all clinical and laboratory data entered on the CRF are complete, accurate and authentic.

Source Data are the clinical findings and observations, laboratory and test data, and other information contained in *Source Documents*. *Source Documents* are the original records (and certified copies of original records); including, but not limited to, hospital medical records, physician or office charts, physician or nursing notes, subject diaries or evaluation checklists, pharmacy dispensing records, recorded data from automated instruments, x-rays, etc. When applicable, information recorded on the CRF shall match the *Source Data* recorded on the *Source Documents*.

12. Ethics:

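### The objective is to validate efficacy, but similar IPSS improvement in two open-label arms without placebo could not show it, and the protocol does not say which result would count

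*Protocol*

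**What the plan says.** - **Objective.** Section 2.1 of the protocol sets out "To validate the efficacy of the XXX" by means of IPSS. It names no comparator, direction or criterion for success.
- **Primary outcome.** Section 6 words it as "validating the efficacy of interventional drug with comparator drug by change in Total International Prostate Symptom Score from baseline to end of treatment".
- **Comparison.** The Study Design section says "The efficacy will be compared with the known Siddha drug XXX". Section 1.2 also speaks only of comparing. Superiority, non-inferiority, equivalence and a margin appear nowhere.
- **Control.** Section 1.2 supports the comparator by tradition ("XXX is a well known Siddha drug and it is in practice since time immemorial") and by an indication matching urinary retention. It gives no trial result and no effect on IPSS in BPH.
- **Blinding and placebo.** Section 3.3 declines blinding because both drugs are classical preparations and a placebo is hard to make. It adds "There is lack in published data" and concludes that the study will be open.
- **Assessment.** Section 9.1.1 says "The Assessment will be made before and after treatment by calculating the International Prostate Symptom Score", then sorts the condition and the response into mild, moderate and severe bands.
- **Size.** Sections 3.2 and 6.4 give 20 subjects, 10 per arm, not counting dropouts.

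**The concern.** The objective claims that the drug works. The design measures a patient-reported score, unblinded, against a control whose own effect on that score is not documented in the protocol. A fall in IPSS within an arm combines any drug effect with response to being treated, regression to the mean and unblinded reporting. If both arms fall by similar amounts, the data cannot distinguish two active drugs from two inactive ones.

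The protocol does not say which result would satisfy the objective. Taken literally, a before-and-after improvement in the investigational arm, alongside a similar improvement in the comparator arm, would meet it. At stake is a published statement that efficacy has been validated when the trial could not have established that.

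**Working it through.** The protocol gives no derivation for its 20 subjects and no SD, effect size, alpha or margin, so there is no figure of its own to reproduce. The main argument is logical; the arithmetic shows what two readings of a no-difference result would be worth.

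**Inputs**
- From the protocol: n = 10 per arm; primary outcome is change in total IPSS from baseline to the end of treatment.
- Assumed, because the protocol is silent: SD of change 4 to 8 points, two-sided 5% tests, and a non-specific improvement of 3 to 6 points common to both arms.

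**Step 1. What similar improvement could mean.**

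| Explanation | Both arms improve? | Arms similar? |
|---|---|---|
| Both drugs active to a similar degree | yes | yes |
| Neither active; non-specific response in both | yes | yes |

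A placebo or untreated arm, or a comparator with a documented IPSS effect, would help to separate these rows. The protocol offers neither. A larger sample would not separate them.

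**Step 2. How easily an inactive drug passes a before-and-after test.** Paired t-test in one arm: 9 degrees of freedom, critical value 2.262, non-centrality = (mean change / SD) × √10. For a common non-specific fall of 5 points:
- SD 4: 5/4 × 3.162 = 3.95, probability of significant improvement 94%
- SD 6: 5/6 × 3.162 = 2.64, probability 65%
- SD 8: 5/8 × 3.162 = 1.98, probability 42%

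With a 3-point fall the probabilities are 56%, 29% and 19%; with a 6-point fall, 99%, 80% and 56%. In every one of these cases the true between-arm difference is zero, and the between-arm test rejects in 5% of trials.

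**Step 3. Whether a non-significant difference could show equivalence.** Half-width of the 95% confidence interval = t(0.975, 18) × SD × √(2/10), with t = 2.101 and √0.2 = 0.447:
- SD 4: 2.101 × 4 × 0.447 = 3.8 points
- SD 6: 2.101 × 6 × 0.447 = 5.6 points
- SD 8: 2.101 × 8 × 0.447 = 7.5 points

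An observed difference of exactly zero would leave open an advantage for either drug of up to 3.8 to 7.5 points. The IPSS total runs from 0 to 35, and the protocol's moderate band (8 to 19) is 11 points from end to end.

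**The case against.** The strongest case against is that the protocol already frames the outcome as a comparison. Section 6 defines it against the comparator, and the Study Design section says efficacy will be compared. On that view the before-and-after sentence in 9.1.1 only says when IPSS is scored, since a between-arm comparison of change needs the same two measurements. The study is labelled Phase 2, and a statistical analysis plan that is not shown may set the test and the reading of a null result.

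Part of this stands. Section 9.1.1 is not a within-arm test, and the choice of test can wait. But what the primary objective claims, and which direction of comparison would bear it out, belong in the protocol, and neither section 6 nor the Study Design section supplies a direction. The Phase 2 label argues for a more modest objective than validation.

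Three stronger readings are tempting and should not be adopted:
- **That the protocol admits the comparator lacks evidence.** The remark on published data in 3.3 follows a sentence about both drugs and serves to justify an open study. It is not tied to the comparator. What can be said is that no comparator effect on IPSS in BPH is cited.
- **That the trial will report equal improvement as validated efficacy, or that this is the likeliest outcome.** Nothing in the text says either. The wording permits such a report; it does not commit to one.
- **That the confidence-interval width is itself the defect.** It reflects the small sample under assumed SDs. It bears on a claim of equivalence. The inability to infer efficacy from equal arms would remain at any sample size.

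**Conclusion.** The concern holds in this limited form. The stated objective claims more than the open-label, placebo-free comparison can show when both arms improve alike, and the wording leaves room for that result to be called validation. This rests on the text alone.

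The figures rest on assumptions. With an SD of change of 4 to 8 points, the between-arm interval at 10 per arm is about ±3.8 to ±7.5 points, so absence of a significant difference would not demonstrate equivalence. With an assumed non-specific improvement of 5 points, an inactive drug would show a significant before-and-after change in 42% to 94% of trials over the same SD range.

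A reader might infer that superiority over the comparator would settle the matter. It would be evidence in the drug's favour, but patients know their treatment and score their own symptoms, so it would remain open to reporting bias.

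**What to change.** Reword sections 2.1 and 6 and the assessment text in 9.1.1 along these lines:

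- The primary result is the difference between the investigational drug and the comparator in change in total IPSS, baseline to the end of treatment, reported with its 95% confidence interval, in an exploratory Phase 2 trial.
- Change within an arm, or a non-significant difference between arms, will not be reported as evidence of efficacy or of equivalence.
- A difference favouring the investigational drug will be described as supportive evidence, subject to open-label reporting bias.
- In 9.1.1, say that the before and after scores, and the severity bands, feed the between-arm comparison or are descriptive.

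This needs no additional patients, arms, visits or data. The downside is a more modest claim than validation.

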5.1 Study drug compliance/adherence

Research subject compliance with the assigned study drug will be recorded in the form during the periodical visits of the study participants.

5.1.1 Withdrawal of subjects due to non-compliance / adherence

During the course of the trial study period if any serious condition develops which requires urgent treatment such subject may be withdrawn from the trial and managed by the principal investigator accordingly.

5.2 Study drug supplies:

Drugs will be procured from SCRI, Chennai. In case, if there is any difficulty, direction may be given to purchase the trial drugs from any GMP certified firms.

5.2.1 Formulation and packaging:

Each drug will be packaged in the packing paper or polythene cover according to the said dosage. It will be given for 15 days. The review of the participants will be advised accordingly.

5.2.2 Mode of dispensing:

The study drugs will be kept in the co investigator's room and dispensed from there.

5.2.3 Drug administration:

Each study drug will be administered as investigator directed procedure. Specific instructions like do's and don'ts, foods which have to be avoided or added and drug compliance will be given to participant during each review.

5.4 Study drug storage and accountability:

Appropriate storage of the study drugs to ensure their stability will be observed by the investigators. Accountability of the study drugs are also done with documentation. Disposition or other destruction of the study drugs upon completion of the study will be done according to the instructions of the investigators.

5.5 Concomitant Medications:

If any infectious illness occurs to the study participants during the trial period, the concomitant medications will be advised by the investigators.

5.5.2 Rescue Medication:

If any problems occur, rescue medication will be governed by the investigators accordingly.

6. Research Study Procedures:

This study is a randomized, comparative, open-labeled comparing the safety and efficacy of XXX and XXX for 12 weeks in 20 patients with *Purasthakola perukkam* [benign prostatic hyperplasia]. The primary outcome measures will be validating the efficacy of interventional drug with comparator drug by change in Total International Prostate Symptom Score from baseline to end of treatment. The secondary outcomes will be evaluation of the safety of the investigational drug, Process Standardization and exploring Siddha clinical parameters of the clinical condition *Purasthakola perukkam* [BPH].

6.1. Screening procedures:

The eligible participants will be enrolled according to the inclusion criteria. The full details of the history and physical examination of the patient will be recorded as per the Proforma (Form 1 & 2) Clinical Assessment will be done on 0, 15, 30,45,60,75 and 90th days (Form 3). Laboratory investigations will be recorded as per the proforma (Form 4) before treatment (0 day), after treatment (at the end of 3rd 6th and 9th month).

6.2 Study drug procedures:

The study arm 1 will receive 100mg of drug with milk q.s after food at morning and night.

The study arm 2 will receive 60 ml of decoction before food at morning and night.

6.3 Follow-up procedures:

Follow ups in both arms will be carried out after 45th and 90th day after completion of 3 months treatment period.

6.4. Schedule of activities (Study table):

Type of study	Randomized, comparative, open labeled clinical study									
Phase	2									
Sample size	20 [without including drop outs, lama]									
Randomization	By appropriate method									
Study arms	Arm 1 => 10 subjects					Arm 2 => 10 subjects				
Intervention	xxx – 100 mg bid with milk after food					xxx- 60 ml bid before food				
Study period	6 months [3 months drug therapy + 3 months follow up]									
Visits		At initial visit (0)	I visit (15 th day)	II visit (30 th day)	III visit (45 th day)	IV visit (60 th day)	V visit (75 th day)	VI visit (90 th day)	Follow up 6 th month	Follow up 9 th month
Arm 1	10 subjects	Screening	Measuring IPSS and other Clinical data	Reporting ADR if any	Reporting ADR if any					
Laboratory investigations		USG,PSA test and other investigations						USG,PSA test and other investigations		
Arm2	10 subjects	Screening	Measuring IPSS and other Clinical data	Reporting ADR if any	Reporting ADR if any					
Data compilation	Data compiled for preparing monograph. Research article will be communicated after compiling the data.									

Safety and Effectiveness Assessments:

7.1 Safety assessment:

Blood and Urine examination will be done to evaluate the safety of the study drug. Laboratory investigations will be recorded as per the proforma (Form 4) before treatment (0 day), after treatment (at the end of 3rd 6th and 9th month).

7.2 Effectiveness assessment:

The IPSS, ultra sonogram study and test for PSA range will be done according to the proforma.

8. Adverse Event Reporting:

8.1 Adverse event definitions:

Adverse event means any untoward medical occurrence associated with the use of the drug in humans, whether or not considered drug related.

Adverse reaction means any adverse event caused by a drug.

Suspected adverse reaction means any adverse event for which there is a reasonable possibility that the drug caused the adverse event. Suspected adverse reaction implies a lesser degree of certainty about causality than “adverse reaction”

Reasonable possibility. For the purpose of IND safety reporting, “reasonable possibility” means there is evidence to suggest a causal relationship between the drug and the adverse event.

Life-threatening, suspected adverse reaction. A suspected adverse reaction is considered “life-threatening” if, in the view of either the Investigator (i.e., the study site principal investigator) or Sponsor, its occurrence places the patient or research subject at immediate risk of death. It does not include a suspected adverse reaction that had occurred in a more severe form and might have caused death.

Serious, suspected adverse reaction. A suspected adverse reaction is considered “serious” if, in the view of the Investigator (i.e., the study site principal investigator) or Sponsor, it results in any of the following outcomes: death, a life-threatening adverse reaction, inpatient hospitalization or prolongation of existing hospitalization, a persistent or significant incapacity or substantial disruption of the ability to conduct normal life functions, or a congenital anomaly/birth defect.

Important drug-related medical events that may not result in death, but life-threatening, or requiring hospitalization may be considered “serious” when, based upon appropriate medical judgment, they may jeopardize the research subject and may require medical or surgical intervention to prevent one of the outcomes listed in this definition. Examples of such medical events include allergic bronchospasm requiring intensive treatment in the

emergency room or at home, blood dyscrasias or convulsions that do not result in inpatient hospitalization, or the development of drug dependency or drug abuse.

Unexpected, suspected adverse reaction. A suspected adverse reaction is considered “unexpected” if it is not listed in the general investigational plan, clinical protocol, or elsewhere in the current IND application; or is not listed at the specificity or severity that has been previously observed and/or specified

